## 2. STUDY BACKGROUND

Breast cancer patients with metastatic disease to the axilla historically have undergone a complete axillary lymph node dissection (ALND); however, this can result in significant morbidity. Alternatively, selective lymph node (SLN) surgery can be performed in patients who receive neoadjuvant chemotherapy (NAC) (1-3), since complete nodal response is seen in 41-74% of these patients (1, 4). The false negative rate of SLN surgery following NAC can be reduced by ensuring removal of a previously biopsy proven malignant lymph node (5). However, without preoperative localization, the biopsied lymph node is not obtained during the SLN surgery in around 23-25% of cases.

Currently at Mayo Clinic Rochester, breast cancer patients who are treated with NAC may have a biopsy clip placed in an axillary lymph node at the time or shortly after percutaneous sampling. Following 12-20+ weeks of NAC, preoperative localization of the sampled lymph node using a radioactive seed can be done up to 5 days prior to surgery. Localization of the sampled lymph node in patients with complete imaging response to NAC can be technically challenging if the biopsy clip is not sonographically visible, and has been shown to be successful in only 72% of cases (6). Here at Mayo, we place sonographically visually enhanced biopsy clips at the time of lymph node sampling; however, there is subset of patients where the clip is not readily identifiable particularly if there is an excellent response to the NAC. Mammographic localization can be achieved only if the biopsy clip can be included in the mammogram. If sonographic or mammographic localization of the biopsy clip is not possible, CT localization may be done, but this increases the cost of care, exposes the patient to a higher radiation dose, and potentially delays surgery.

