### 3. STUDY AIMS

**Aim 1:** Evaluate if Magseed is a viable alternative to radioactive seed as a localization method for biopsy proven metastatic breast carcinoma following neoadjuvant chemotherapy.

**Aim 2:** Determine the amount of artifact created by the Magseed in the axilla at MRI and identify imaging optimization to minimize the artifact produced by the magnetic clip.

**Aim 3:** Assess the success of retrieval of the Magseed and biopsy proven metastatic lymph node in the operating room compared to the current practice with the radioactive seed.

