Phase 2 participants will enroll in the study prior to NAC and have routine contrast enhanced breast MRIs performed before and after NAC. Clinically indicated MRI scans will be charged to the patient's insurance company as this imaging is standard clinical practice. The MRI protocol will use our standard clinical sequences (axial ideal T1 and T2-weighted, axial STIR, and axial 3D vibrant using a dedicated breast coil). Once contrast is injected (gadobutrol 10mmol/10mL) 3D vibrant sequences will be obtained four times after contrast injection (FOV 28 cm or to fit the patient size, and an image-thickness/image-increment of 5mm/1mm).

**Mammogram:** Patients enrolled in the research study will have standard mammographic imaging before and after NAC, which will include both the breast and axilla as per routine clinical protocol.

**Ultrasound:** Patients enrolled in the research study will have standard sonographic imaging before and after NAC of the breast and axilla as per routine clinical protocol. Post-NAC ultrasound of the axilla will be a supplemental assessment to breast MRI as the Magseed artifact may obscure these findings.

**Seed Removal:** As per the current practice, patients will have targeted axillary lymph node dissection including both the localized lymph node and sentinel lymph node. Identifying the lymph node containing the Magseed will require the Sentimag handheld probe in the operating room. This device which functions similar to the gamma probe has been approved for an equipment trial starting in August of 2018. Once the lymph node has been excised a specimen radiograph will be obtained to verify removal.

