## 8. END OF STUDY DEFINITION

A participant is considered to have completed the study once the Magseed has been removed from the axilla.

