## 10. DATA MANAGEMENT & STATISTICAL CONSIDERATIONS

**Data Management:** The principle investigator and co-investigators will supervise the data collection management.

**Outcome analysis:** The successful placement of the Magseed into the metastatic axillary lymph node will be evaluated and recorded by the radiologist performing the procedure. This information will be document into the electronic medical records as per normal clinical practice, in addition this information stored in the database.

The degree in which the artifact created by the Magseed in the axilla obscures the axillary or adjacent breast findings will be evaluated and recorded by the radiologist interpreting the MRI. Treatment response based on mammographic and sonographic evaluation of the axilla will be evaluated and recorded by the radiologist. The radiologist will determine if the supplemental imaging with mammography and sonography adequately replaces visualization of the axilla on MRI. Imaging results will be records in standard radiological reports as well as the database.

The successful retrieval of the Magseed into the metastatic axillary lymph node will be evaluated by the surgeon and radiologist. These results will be reported in both the patients operative report as well as the research database.

**Adverse events:** Adverse events occurring during the research study will be recorded into the electronic medical records and recorded into the research database.

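### Does one retrieval sentence in Section 10 leave it unproven that the excised seeded node is the biopsied node?

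*Combined protocol and SAP*

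**What the plan says.** Aim 3 in Section 3 is to "Assess the success of retrieval of the Magseed and biopsy proven metastatic lymph node" in the operating room and to compare this with radioactive-seed practice. Section 10 (Outcome analysis) turns it into one sentence: "The successful retrieval of the Magseed into the metastatic axillary lymph node will be evaluated by the surgeon and radiologist". The result goes into the operative report and the research database.

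Three other provisions bear on whether the right node came out:

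- **Placement.** Section 5 confirms the seed's position after deployment by ultrasound and by mammography with tomosynthesis. Section 10 makes successful placement in the metastatic node a recorded result of its own, entered by the radiologist who placed the seed.
- **Surgery.** Section 5, Seed Removal: "Identifying the lymph node containing the Magseed will require the Sentimag handheld probe in the operating room". The operation is a targeted dissection that takes the localized node and the sentinel node.
- **Verification.** Same paragraph: "Once the lymph node has been excised a specimen radiograph will be obtained to verify removal".

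Section 2 says that patients may have a clip placed in the node at or soon after sampling, and that this site uses clips made to be visible on ultrasound. Section 4 does not make a clip an eligibility criterion.

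**The concern.** The clinical rationale is about the node. Section 2 states: "The false negative rate of SLN surgery following NAC can be reduced by ensuring removal of a previously biopsy proven malignant lymph node". The failure rate it gives is also for the node: "without preoperative localization, the biopsied lymph node is not obtained during the SLN surgery in around 23-25% of cases". Seed retrieval shows how the device performed; node retrieval shows whether the patient had the operation that the rationale calls for. Aim 3 keeps the two apart and Section 10 appears to merge them.

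The steps around surgery lean on the seed. The probe finds the node by its seed, and Section 8 closes participation on the seed: "A participant is considered to have completed the study once the Magseed has been removed from the axilla". A radiograph that shows only a seed proves that the seed is out, not that the tissue around it was biopsied months earlier. Pathology often cannot settle the matter through residual tumour, because Section 2 reports that "complete nodal response is seen in 41-74% of these patients". Part 1 looks most exposed: the seed goes in after chemotherapy, when Section 2 says the clip can be hard to find.

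At stake would be a retrieval rate that hides a seed in the wrong node, in a study so small that one patient visibly moves the result.

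**Working it through.** The plan states no rate, threshold, power or sample-size calculation for retrieval, so there is no figure to reproduce. The check is mainly of the text.

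**1. What can the sentence mean?** Let S be seed retrieved, N biopsied node retrieved, and P seed recorded as placed in the metastatic node.

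- *Joint reading:* success means S and N. A seed known to have been in another node is then a failure, and since (S and N) cannot exceed N, the reported rate is a conservative figure for node retrieval.
- *Seed-only reading:* success means S. But P is recorded separately for every patient. P, then excision of the node containing the seed (Section 5), gives N, on two conditions: the placement call was right and the seed stayed in the node.

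On either reading, node retrieval can be derived from recorded items. What is unwritten is the link between them.

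**2. Do the other passages pull the outcome towards the seed?** Not much. The specimen-radiograph sentence is about the excised node. The Section 8 sentence defines when a participant has finished; it is not an outcome. Residual tumour is not proposed anywhere as evidence of identity, so the 41-74% response rate counts against a method the plan does not use.

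**3. How far does one patient move the result?** Exact (Clopper-Pearson) 95% limits. When all n succeed the lower limit is 0.025^(1/n):

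| Result | 95% limits |
|---|---|
| 20/20 | 0.025^(1/20) = 83.2% to 100% |
| 19/20 | 75.1% to 99.9% |
| 10/10 (one Part) | 0.025^(1/10) = 69.2% to 100% |
| 9/10 (one Part) | 55.5% to 99.7% |

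These show what any single reclassification does at this sample size. They do not measure a fault in the wording. Nor is 100% - (23 to 25%) = 75-77% a benchmark for Aim 3: it describes surgery without localization, while Aim 3 compares with radioactive seeds.

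**4. How likely is a mismatch at all?** The documents give no rate for a retrieved seed in the wrong node. The 72% in Section 2 is the success rate of finding the sampled node after chemotherapy and cannot stand in for it. With an assumed rate q, the chance of at least one mismatch is 1 - (1 - q)^n:

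| q (assumed) | n = 10 | n = 20 |
|---|---|---|
| 2% | 18% | 33% |
| 5% | 40% | 64% |
| 10% | 65% | 88% |

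So a mismatch could occur. Whether it is *recognised* depends on the placement images, the specimen radiograph and any clip. Splitting one database item into two adds none of that evidence. A recognised mismatch is not a success under the joint reading and shows up in P under the other; an unrecognised one would be scored as node retrieved in a second field too.

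**5. Is the absence of separate fields established?** No. The collection form is not part of the document, and the Data paragraph in Section 11 speaks of the collection instruments as still to be designed.

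**The case for a change.** The strongest reply is that deriving N from P relies on one radiologist's own call and on the seed not moving, which in Part 2 must hold through the whole of chemotherapy. The plan does not write the derivation down, and two readers could score the same patient differently. A clip seen beside the seed in the specimen would be independent evidence, yet a clip is not required and the radiograph has no stated reading rule. Node identity not noted at surgery may be hard to recover later. Aim 3 also compares with radioactive-seed practice, which needs one definition that can be applied to both.

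Most of this is true as description. It stands that Section 10 gives no criterion and that a written one would make the report clearer, chiefly by separating patients whose node was confirmed from those in whom it was inferred. It does not show that following the plan gives a wrong answer. The surgeon and the radiologist judge retrieval with the radiograph available, and a clip, where there is one, is a natural thing to look for on it: Section 2 already treats clips as targets for mammographic localization. The comparison with radioactive seeds raises the wider question of which data are used for that practice, and splitting the retrieval item would not answer it.

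**Conclusion.** No change to the plan is needed. The wording is loose and one link is left unstated, but the items needed to report seed and node retrieval are already collected: placement into the metastatic node, excision of the node carrying the seed, a specimen radiograph, and a judgement by two disciplines. Any sensible analyst would tabulate placement against retrieval by Part and say where a clip confirmed the node.

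No bias can be shown, so no size can be given. The only scale available is the effect of one patient in 20 (lower limit 83.2% against 75.1%), in a descriptive pilot with no threshold to cross.

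This rests on three assumptions: the placing radiologist's record is generally correct, the seed generally stays in the node, and the surgeon and radiologist would not call a seed known to be in another node a success. The first two are not tested in the documents, and a second database field would not test them either. The third follows from Section 10, which names the metastatic node in the retrieval item itself.

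### The retrieval outcome does not separate nodes located by the Sentimag probe from nodes removed as sentinel nodes, so crude retrieval only weakly measures localization

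*Combined protocol and SAP*

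**What the plan says.** The retrieval outcome is defined in Section 10 (Outcome analysis) of the combined protocol and SAP: "The successful retrieval of the Magseed into the metastatic axillary lymph node will be evaluated by the surgeon and radiologist". On recording, it adds: "These results will be reported in both the patients operative report as well as the research database". It gives no criterion for success, no item for the route by which the node was found, and no threshold.

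Section 5 (Seed Removal) describes the operation. In it, "patients will have targeted axillary lymph node dissection including both the localized lymph node and sentinel lymph node"; inclusion criterion 3 in Section 4 matches this. On detection, the section says: "Identifying the lymph node containing the Magseed will require the Sentimag handheld probe in the operating room". On confirmation, it says: "Once the lymph node has been excised a specimen radiograph will be obtained to verify removal".

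Section 2 gives the background rate: "without preoperative localization, the biopsied lymph node is not obtained during the SLN surgery in around 23-25% of cases".

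Aim 1 (Section 3) asks whether the Magseed is a viable alternative to the radioactive seed for localization. Aim 3 is to "Assess the success of retrieval of the Magseed and biopsy proven metastatic lymph node in the operating room compared to the current practice"; that practice is radioactive seed localization. No retrieval rate for radioactive seed practice is given.

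**The concern.** Aims 1 and 3 concern a localization device, but the outcome scores removal. Two procedures that can each bring out the seeded node take place in the same operation: probe-guided excision and sentinel node removal. As Section 10 is written, a node removed because it took up the sentinel tracer scores the same as one that the surgeon found by its magnetic signal.

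This would not matter much if sentinel surgery seldom obtained the biopsied node. By the protocol's own figure, it does so about three times in four. A good retrieval count could then arise with little contribution from the seed, and failures of detection could sit unseen inside it. Detection is of most interest in Part 2, where the seed is in place throughout neoadjuvant chemotherapy (NAC) before anyone searches for it. The route of detection is also hard to reconstruct later if it was not recorded at the operation.

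**Working it through.** **Inputs**
- Biopsied node not obtained by sentinel surgery without localization: 23-25% (Section 2).
- Patients: 20 in total (Section 1), 10 in Part 1 and 10 in Part 2 (Section 5).
- Success threshold, retrieval rate with radioactive seeds, and pooled analysis: none stated.

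The 23-25% comes without underlying counts, so it cannot be reproduced from the documents. The sample size has no stated error rates or target, so there is no calculation to reproduce there either.

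**Step 1. Background retrieval rate**

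1 − 0.25 = 0.75 and 1 − 0.23 = 0.77.

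Expected retrievals with no contribution from the seed:
- of 20: 20 × 0.75 = 15.0 to 20 × 0.77 = 15.4
- of 10: 7.5 to 7.7

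**Step 2. How often would a good result arise from the background alone?**

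With X binomial(n, p), P(X ≥ r) is the sum over k = r to n of C(n, k) p^k (1 − p)^(n − k). Two examples:
- 10/10: 0.75^10 = 0.056 and 0.77^10 = 0.073
- 9 or more of 10 at p = 0.75: 10 × 0.75^9 × 0.25 + 0.75^10 = 0.188 + 0.056 = 0.244

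The last column is the exact (Clopper-Pearson) two-sided 95% interval when the observed count equals r. When all n are retrieved, its lower limit is 0.025^(1/n): 69.2% for n = 10 and 83.2% for n = 20.

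| Result | P at 0.75 | P at 0.77 | Exact 95% interval at that count |
|---|---|---|---|
| ≥8/10 | 0.526 | 0.586 | 44.4-97.5% |
| ≥9/10 | 0.244 | 0.292 | 55.5-99.7% |
| 10/10 | 0.056 | 0.073 | 69.2-100% |
| ≥18/20 | 0.091 | 0.128 | 68.3-98.8% |
| ≥19/20 | 0.024 | 0.037 | 75.1-99.9% |
| 20/20 | 0.003 | 0.005 | 83.2-100% |

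Within a Part, no result has an interval that excludes 75-77%, not even a perfect one. Pooled, 18/20 does not exclude it. For 19/20 the lower limit is 75.1%, just above 75% but below 77%. For 20/20 it lies above the whole range.

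**Step 3. Effect on the comparison in Aim 3**

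Let q be the probability that the localizer leads the surgeon to the node, and b the probability that sentinel surgery obtains the node when the localizer does not. Then

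retrieval = q + (1 − q) b.

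With the same b for both devices, the difference in retrieval is

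(q_Magseed − q_radioactive) × (1 − b).

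If b = 0.75-0.77, then 1 − b = 0.23-0.25. Only about a quarter of any true difference in localization would show in crude retrieval. Taking b at the background rate is an assumption; the documents do not say how often sentinel surgery obtains the node when a localizer fails.

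**The case against.** **The plan ties removal to the probe.** Section 5 makes the Sentimag probe the means of identification, followed by excision and a specimen radiograph. On this reading, retrieval is probe-guided by design. This stands as a description of the intended procedure. But it is neither a scoring rule nor a data item, and the radiograph confirms that the seed is out, not how it was found. The gap is that departures from the intended path are not specified as something to capture.

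**The comparator is the radioactive seed, not absence of localization.** This is correct, and current practice also includes sentinel removal, so the background is present on both sides. It does not rescue the outcome, because a shared background compresses the difference, as Step 3 shows.

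**Near-perfect results are plausible.** Section 4 of the background discussion need not be invoked beyond this: Section 2 reports a 100% success rate for the Magseed in non-palpable breast lesions. A reader might infer from the 75-77% that no high retrieval rate could show that the Magseed worked. The documents do not support that: 20/20 pooled would be very unlikely at the background rate. Even so, pooling joins two Parts with different seed timing, the protocol states no pooled analysis, and 20/20 would not show for any one patient that the probe found the node.

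**Particular failure mechanisms are conjecture.** A reader might suppose that the signal weakens during NAC, or that seeds will turn up in a wider dissection specimen. Neither is in the documents: Section 2 describes the seed as cleared for long-term placement, and Section 5 describes only targeted dissection. The point does not rest on them.

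**The route may be recorded anyway.** Section 10 lists no fields for any outcome, and the data collection instruments mentioned in Section 11 are not shown. So one can say that the route is not specified, not that it will go unrecorded.

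**This is a pilot of 20 with no hypothesis test.** That limits the weight of the point, but a descriptive pilot still needs an outcome that measures its aim.

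**Conclusion.** The concern holds in a limited form. Retrieval as defined in Section 10 mixes localization by the seed with incidental removal as a sentinel node, and so measures localization only weakly. At a background of 75-77%, neither a perfect result in one Part (probability 0.056-0.073) nor 18 or more of 20 pooled (0.09-0.13) can be separated from sentinel surgery alone. Pooled 20/20 can, and 19/20 is borderline. The outcome is therefore not uninformative, but most results that would be called good leave the seed's contribution open.

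This rests on three assumptions: the Section 2 rate, which has no reference attached to its sentence, applies to these patients; patients are independent; and retrieving the seed amounts to retrieving the biopsied node. The pooled figures also treat the two Parts as one sample.

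**What to change.** Add a definition and a few items to Section 10. They concern recording and scoring only and leave surgical conduct as it is.

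1. The surgeon records at operation:
   - what first identified the seeded node (Sentimag signal, sentinel tracer, palpation, other);
   - whether a Sentimag signal was detected;
   - whether the node was also a sentinel node.
2. Report by Part, with exact intervals:
   - (a) retrieval in which the Sentimag signal first identified the node and the specimen radiograph confirmed the seed;
   - (b) any retrieval, read against the 75-77% background.

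The word *first* matters in (a). Without it, a node found by tracer and then checked with the probe would still count as a localization success. Conversely, (a) can miss a working seed if the tracer happened to lead to the node first, which is why signal detection is recorded separately.

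The cost is two or three extra data fields and one definition. The small downside is that (a) may be lower than crude retrieval.

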## 11. ETHICAL CONSIDERATIONS

**Informed Consent:** Institutional Review Board (IRB)-approved consent forms will be given to the participants. That participants will asked to read the form. The research study will be explained to the participant and all questions will be answered by the principle investigators, co-investigators, and/or study coordinator. A verbal explanation will be provided in terms

suited to the participant's comprehension of the purposes, procedures, and potential risks of the study and of their rights as research participants. Participants will be informed that participation is voluntary and that they may withdraw from the study at any time, without prejudice. Participants will have the opportunity to carefully review the written consent form and ask questions prior to signing. The participants should have the opportunity to discuss the study with their family or surrogates or think about it prior to agreeing to participate. The consent form must be signed by the subject or the subject's legally authorized representative, and the individual obtaining the informed consent. A copy of the informed consent document will be given to the participants for their records. The informed consent process will be conducted and documented in the source document (including the date), and the form signed, before the participant undergoes any study-specific procedures. The rights and welfare of the participants will be protected by emphasizing to them that the quality of their medical care will not be adversely affected if they decline to participate in this study.

**Confidentially:** Protected patient health information will be kept in a locked file cabinet. An enrollment log will be maintained confirming informed consent was obtained. A key linking patient identifiers to their research study identifier will be kept secure. Identifiable information will not appear on any reports, publications, or other disclosures of the study outcomes. Every effort will be made to keep medical information confidential.

**Records:** The principal investigator will maintain records and essential documents related to the conduct of the study as outlined in the Mayo Clinic Research Policy Manual – "Retention of and Access to Research Data Policy" [http://mayocontent.mayo.edu/research-policy/MSS\\_669717](http://mayocontent.mayo.edu/research-policy/MSS_669717) . These will include subject case histories and regulatory documents.

**Data:** Study data will be used to design the data collection instruments and patient data will be entered into a SDMS Database by the study coordinator or other members of the study team. The data collected in will later be exported to the appropriate software for statistical analyses.

**Publications:** Results from this study will be published in a peer reviewed journal.

